### **3.0 Objectives**

A. **Primary Objective:** To estimate the proportion of patients who achieve a clinically significant improvement in erectile dysfunction (ED) when treated with a combination of Atorvastatin or patient's currently prescribed statin, Vitamin E, and Pentoxifylline (PAVE). Clinically significant improvement is defined as an improvement by one category, e.g., from mild-moderate to mild, on the IIEF-5 [International Index of Erectile Function] score, in men with established ED who have completed radiation therapy for prostate adenocarcinoma.

B. **Secondary Objectives**

- i. To report the safety profile of PAVE.
- ii. To report the rate of choosing other ED treatments after PAVE.

### **4.0 Patient Selection**

**Subject Inclusion Criteria:**

1. Histologically or cytologically confirmed diagnosis of adenocarcinoma of the prostate
2. Previous radiation therapy (any form) with curative intent for prostate cancer
3. Erectile dysfunction, as determined by an IIEF-5 score of <22
4. Normal testosterone (including men on testosterone replacement), defined as testosterone >150 ng/dl at the time of screening
5. Age  $\geq$ 18 years

6. Karnofsky Performance Status (KPS)  $\geq 70$ , or ECOG 0-2
7. Patients may be taking an HMG-coA-reductase inhibitor
8. Serum alanine aminotransferase (ALT) and aspartate aminotransferase (AST)  $\leq 3X$  upper limits of normal (ULN)
9. Creatinine Kinase  $< 5$  times ULN.
10. Normal renal function as defined below:

Normal renal function is defined as creatinine clearance  $\geq 30$  ml/min via the Cockcroft Gault Formula:

$$\text{Female CrCl} = \frac{(140 - \text{age in years}) \times \text{weight in kg} \times 0.85}{72 \times \text{serum creatinine in mg/dL}}$$

$$\text{Male CrCl} = \frac{(140 - \text{age in years}) \times \text{weight in kg} \times 1.00}{72 \times \text{serum creatinine in mg/dL}}$$

**Subject Exclusion Criteria:**

1. No androgen deprivation therapy within the past 12 months
2. No contraindication to an HMG-coA-reductase inhibitor, Vitamin E or Pentoxifylline
3. Not currently taking cyclosporine, the HIV protease inhibitors, hepatitis C protease inhibitors, Gemfibrozil, other fibrates, Clarithromycin, itraconazole or strong inhibitors of CYP3A4
4. No recent cerebral or retinal hemorrhage that in the opinion of the treating physician would make PAVE unsafe (within 6 months)
5. No current chemotherapy during study participation
6. No active liver or muscle disease that in the opinion of the treating physician would make PAVE unsafe.
7. No prior radical prostatectomy, cystoprostatectomy, abdominoperineal resection or retroperitoneal lymph node dissection

8. Not currently taking a 5PDE inhibitor nor have used one within 30 days of enrolling in the study
9. No recent deep venous thrombosis, myocardial infarction or pulmonary embolism (within 6 months) requiring continued anticoagulation other than ASA.
10. No cardiac arrhythmias or artificial heart valves requiring anticoagulation other than ASA.
11. No concurrent drugs with anti-platelet properties (e.g., P2Y12 inhibitors, non-steroidal anti-inflammatory agents, selective serotonin reuptake inhibitors) other than low dose ASA (81mg/d).
12. Not currently taking high dose statin therapy, defined as Rosuvastatin >10mg/d or Atorvastatin >40mg/d.
13. Not currently taking theophylline
14. No history of active peptic ulcer disease in the past 6 months.
15. no history of intolerance to pentoxifylline or methylxanthines such as caffeine, theophylline and theobromine that in the opinion of the treating physician would make PAVE unsafe.
16. No concurrent use of CYP1A2 inhibitors (e.g., ciprofloxacin), ketorolac, or vitamin K antagonists (e.g. warfarin).

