Statins have been studied for a role in the treatment of established ED, although, until recently, not in the setting of radiation induced ED. A recent meta-analysis of all trials investigating the efficacy of Statin use on non-radiation induced ED showed a clinically and statistically significant increase of 3.4 points on the IIEF. Of note, this was roughly 1/3 to ½ of the effect seen with PDE inhibitors. The most commonly used statins were atorvastatin followed by simvastatin. Statins improve endothelial function both by lowering LDL (low density lipoprotein) levels and by increasing the availability of NO. Thus, statins appear to counteract one of the primary molecular processes implicated in the development of radiation induced ED. A recent secondary analysis of a trial studying the ability of lovastatin to prevent radiation induced rectal injury demonstrated that this agent was effective in preserving erectile function across most domains of the IIEF with a minimum of 2 years follow-up. More potent statins, such as atorvastatin, might prove even more effective in this setting.

As noted above, along with decrease in NO production resulting from the inflammatory response to RT, fibrosis also appears to be a component of radiation induced ED. As such, the combination of Vitamin E and Pentoxifylline may provide a benefit as this combination has a proven role in the treatment of established soft tissue fibrosis from radiation. These drugs have been used for radiation induced proctitis as well as cystitis. Additionally, a recent study has shown that prophylactic Vit E and Pentoxifylline reduces the rate of post-mastectomy fibrosis and implant loss in women with breast cancer. Thus, the addition of Vitamin E plus Pentoxifylline to atorvastatin, as proposed in this study, will target both the proinflammatory and profibrotic pathways known to play a role in late radiation injury.

Another rationale for the combination of these agents is their well-established favorable side effect profile. All of these agents have been used for many years in the clinic and are generally well-tolerated. In addition, are all off-patent and are less costly than the 5-PDE inhibitors.

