## **5.0 Pre-treatment evaluation**

(must be completed within 8 weeks prior to the completion of second step enrollment in CORe; In the event that a patient cannot be seen in person to consent and is consented remotely, physical exam and vitals are not required prior to enrollment. KPS/ECOG maybe conducted from the telephone calls. Baseline labs could be drawn at outside facility and IIEF-5 questionnaire can be completed at home and both can be submitted via secure email or fax.)

A. History and Physical, including KPS or ECOG. Include the following information at a minimum:

1. Age
2. Race and ethnicity
3. T-stage, N-stage, M-stage, Gleason score, initial PSA, PSA prior to radiation
4. Radiation therapy details:

- a. treatment dates
- b. modality: protons, photons, brachytherapy (include isotope used and dose), or any combination of these modalities
- c. for external beam (photon, proton, or combination):
  - 1. include whether or not pelvic lymph nodes were treated, and if so, report total and daily dose/fraction
  - 2. report total dose and dose per fraction for treatment to prostate +/- seminal vesicles
- 5. Most recent androgen deprivation therapy: report dates of treatment and drugs used
- 6. smoking history
- 7. alcohol history
- 8. current medications including non-prescription substances will be recorded in the medical chart.
- 9. Most recent treatment tried for ED
- 10. complete past medical history including history or presence of diabetes mellitus, hypertension, hyperlipidemias, endocrinopathies, cardiovascular diseases (e.g., coronary artery disease, CVA, TIA), hematologic diseases and psychiatric conditions will be recorded in the medical chart.
- 11. history of prior abdominal &/or pelvic surgery
- 12. current relationship status (i.e., married, widowed, divorced, presence of significant other)

B. Baseline assessment of erectile function using IIEF-5.

C. Laboratory studies: serum testosterone, CK, liver panel, BUN, Creatinine, GFR estimation, CBC, INR, PT, PTT

D. Baseline CTCAE V4.03 items grade 2 or higher: blurry vision, abdominal distension, abdominal pain, bloating, diarrhea, dyspepsia, flatulence, gastrointestinal pain, nausea, vomiting, malaise, pharyngitis, urinary tract infection, bruising, arthralgias, bone pain, generalized muscle weakness, myalgia, headache, rash (maculopapular), flushing

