## **6.0 Registration Procedures**

This protocol utilizes a two-step enrollment in the MD Anderson Cancer Center CORe database.

Patients should be entered into the first-step CORe enrollment when consents are completed.

Upon completion of all required materials for enrollment, second step enrollment will be completed to fully enroll the patient in CORe. No protocol-related therapies may be administered until the patient is fully enrolled in CORe.

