**Table 1: Patient assessment schedule**

Test	Baseline *** (within 8 wks of enrollment)	6 wk* ± 2 wks	3 mo* ± 2 wks	6 mo* ± 2 wks	9 mo* ± 2 wks	12 mo* ± 2 wks	18 mo ± 4 wks*
H&P	X			X		X	X
BP, Pulse, Respiratory Rate	X	X	X	X	X	X	
KPS or ECOG	X			X		X	
IIEF-5****	X		X	X	X	X	
CTCAE V4.03**	X	X	X	X	X	X	
Hepatic panel	X	X	X	X	X	X	
CK 	X	X	X	X	X	X	
BUN, Creatinine, calculated GFR, CBC, PT, PTT, INR, Testosterone	X	X	X	X	X	X	

In addition to scheduled testing, obtain at any time patient notes muscular symptoms

\*follow up times start from the day patient begins taking all 3 drugs concurrently. Can be done over the phone or in person, in the event that follow up can only be done over the phone, physical exam, KPS or ECOG, and vitals do not have to be obtained. Labs could be drawn at outside facility and IIEF-5 questionnarire can be completed at home and both can be submitted via secure email or fax.

\*\*selected items with CTCAE grade 2 or higher: blurry vision, abdominal distension, abdominal pain, bloating, diarrhea, dyspepsia, flatulence, gastrointestinal pain, nausea, vomiting, malaise, pharyngitis, urinary tract infection, bruising, bleeding, arthralgias, bone pain, generalized muscle weakness, myalgia, headache, rash (maculopapular), flushing, chest pain, palpitations, dyspnea, cough, wheezing, lower extremity edema. This assessment can be done either over the phone or in person.

\*\*\*please refer to section 5.0 for pre-treatment evaluation

\*\*\*\*please refer to the appendix for the IIEF-5 questionnaire

D. **Modification of statin dosing**

1. discontinue if transamimases become  $\geq$  3 times ULN
2. discontinue if creatine kinase becomes  $\geq$  5 times ULN
3. If not on a statin prior to enrollment in the trial, discontinue if signs or suspicion of cardiovascular issues appear per the discretion of the treating physician.

For other side effects listed in section 8 above:

- a. if dose is  $\geq$ 20mg and if toxicity is Grade 2, decrease dosage by 50%. If toxicity resolves or decrease to Grade 1, maintain atorvastatin at this lower dose. If toxicities are  $\geq$ Grade 3, stop atorvastatin and the patient should be removed from the study.
- b. If dose=10mg, hold atorvastatin. If toxicity resolves or decrease to Grade 1, restart at 10 mg every other day. If toxicities are  $\geq$ Grade 3, stop atorvastatin and the patient should be removed from the study.

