## **B. Endpoints**

### **i. IIEF-5 (International Index of Erectile Function)**

This validated instrument will be completed as per study calendar. The instrument categorizes ED severity into 5 categories as none (22-25), mild (17-21), mild to moderate (12-16), moderate (8-11), or severe (5-7). A patient will demonstrate improvement at any time point if his score goes up enough to move at least 1 category less severe compared to baseline. A patient with improvement will be considered to have a response. Patients who drop out of the trial without any measurements will count as a non-responder.

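### The baseline IIEF-5 can precede the PDE5-inhibitor-free period if exclusion 8 refers to second-step enrolment; the resulting bias is probably downward, and its size is unknown and may be small

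*Combined protocol and SAP*

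**What the plan says.** Section 5.0 states that the pre-treatment evaluation "must be completed within 8 weeks prior to the completion of second step enrollment in CORe". Item B of that evaluation is the "Baseline assessment of erectile function using IIEF-5", with no condition about PDE5 inhibitor use. Table 1 gives the same 8-week window and calls its anchor simply enrolment.

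Section 4.0, exclusion 8, reads: "Not currently taking a 5PDE inhibitor nor have used one within 30 days of enrolling in the study". It does not name an enrolment step.

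Section 6.0 has two steps. For the first, "Patients should be entered into the first-step CORe enrollment when consents are completed". After all required materials are in, "second step enrollment will be completed to fully enroll the patient in CORe".

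Section 11.0 B.i counts a man as improved at any time point if "his score goes up enough to move at least 1 category less severe compared to baseline". The Trial Summary (1.0) gives the type of control as each patient's own baseline, so there is no concurrent arm. The same response definition feeds the futility rule in 11.0 D.

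Section 5.0.A.8 has current medications recorded in the chart. Section 5.0.A.9 records the latest ED treatment but asks for no date. By contrast, 5.0.A.5 does ask for dates of androgen deprivation.

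**The concern.** The two windows have different lengths and may share the same anchor. The longer one governs the measurement on which the primary endpoint rests; the shorter one governs the drug most likely to raise that measurement. No sentence requires the questionnaire to follow the drug-free period or to be repeated before treatment.

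A man whose reference score was obtained on a PDE5 inhibitor, and who is then followed off it, has to regain the lost drug effect before any benefit of PAVE can show as a category gain. With no control arm, nothing offsets this. The primary proportion would be too low, and the futility rule would act on the same understated counts.

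**Working it through.** **Inputs.** Baseline window 8 weeks = 56 days (5.0, Table 1). PDE5-inhibitor-free period 30 days (exclusion 8). IIEF-5 categories 5-7, 8-11, 12-16, 17-21 and 22-25 (11.0 B.i). Eligibility score below 22 (4.0). Statin effect 3.4 points on the IIEF, of which section 2.0 says "this was roughly 1/3 to ½ of the effect seen with PDE inhibitors". Prior Beta(0.33, 0.67), N = 50, futility bounds 0/10, 2/20, 5/30 and 7/40 (11.0 C and D).

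**1. The plan's own figures.** The posterior is Beta(0.33 + x, 0.67 + n - x).
- For 16/50 the 95% interval is 20.1% to 45.3% (width 25.2 points); for 17/50 it is 21.8% to 47.4%. Both match 11.0 C.
- Applying the 0.975 rule at 10, 20, 30 and 40 patients returns bounds 0, 2, 5 and 7, as printed.
- An exact binomial calculation over the four looks, with toxicity and response independent and true toxicity 10%, gives early-stop probabilities of 0.814, 0.277 and 0.063 at response rates 15%, 25% and 33%. The plan prints 0.81, 0.28 and 0.06. At this toxicity almost all early stopping is for futility: the plan's table shows only 0.001 at a 55% response rate.

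**2. The timing gap.** If enrolling means the second step: 56 - 30 = 26 days, that is days -56 to -31. If it means the first step, at consent, a form completed after consent falls in the drug-free period. What then remains is a form completed before consent, which 5.0 does not expressly rule out.

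**3. Size for one affected man.** The PDE5 effect implied by section 2.0 is 3.4/(1/2) = 6.8 to 3.4/(1/3) = 10.2 points. A 3.4-point gain measured from an on-drug baseline then appears as 3.4 - 6.8 = -3.4 to 3.4 - 10.2 = -6.8 points. In whole-number scores, keeping only men whose on-drug score stays below 22:

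| PDE5 effect | Gain on PAVE | Eligible off-drug scores | Truly gain a category | Scored as response |
|---|---|---|---|---|
| 7 | 3 | 10 | 7 | 0 |
| 10 | 3 | 7 | 6 | 0 |
| 7 | 8 | 10 | 10 | 2 |
| 10 | 8 | 7 | 7 | 0 |

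These rows assume that every man has the same gain, without measurement noise, and that a figure for statins in non-radiation ED carries over to PAVE and to the IIEF-5.

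**4. Size for the trial.** Let f be the share of would-be responders missed. The observed rate is 0.33 × (1 - f). The documents give no f.

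| f | Observed rate | Early-stop probability |
|---|---|---|
| 0 | 33.0% | 6.3% |
| 2% | 0.33 × 0.98 = 32.3% | 7.2% |
| 5% | 0.33 × 0.95 = 31.4% | 8.8% |
| 10% | 0.33 × 0.90 = 29.7% | 12.2% |

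If affected men are as likely as others to be would-be responders, and each affected responder is missed, f is also the share of all men affected: one man in 50 is 2%, five in 50 are 10%.

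**The case against.** **The gap depends on one reading.** Exclusion 8 does not name a step, and first-step entry takes place at consent. On that reading the gap largely closes. This stands. The step-two anchor in 5.0, the unqualified use of enrolment in Table 1 for the same window, and the description of step two as full enrolment favour the other reading but do not decide it. A reader might infer that the plan definitely admits on-drug baselines; the text supports only that it may.

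**The route is narrow.** Exclusion 8 also bars current users, and the evaluation that contains the IIEF-5 records current medications and the latest ED treatment. A site would have to see current use, keep the form, and enrol the man later without a repeat. This reduces the likely frequency, but the text does not forbid that sequence.

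**Follow-up may not be off the drug.** A reader might infer that every follow-up score is drug-free. The text contains no ban on PDE5 use during the study. Section 11.0 B.iii collects ED drugs prescribed during the trial or on leaving it. Section 11.0 E counts men who leave to begin such a drug, which hints that starting one ends participation but is not a prohibition. The downward direction therefore holds only for men who are off the drug at follow-up.

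**The pool of recent users may be small.** Section 2.0 calls these drugs the usual first-line treatment, but the same paragraph says that cost puts them out of reach of most patients. The documents do not settle how many recruits are recent users.

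**Conclusion.** The concern holds as a conditional one. If exclusion 8 refers to second-step enrolment, there are 26 days in which an eligible man may give an on-drug baseline, and no rule corrects it. For such a man, if he is off the drug at follow-up, the chance of being counted as a responder falls, so the primary proportion is biased downward and a futility stop becomes more likely.

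The size for the whole trial is unknown and may be small. Even at f = 10% the estimate moves by 33.0 - 29.7 = 3.3 points, against a credible interval about 25 points wide; the early-stop probability roughly doubles, from 6.3% to 12.2%.

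Two stronger readings are not supported. The contrast of 7 in 10 (or 6 in 7) true gains against none scored might suggest that an affected man can never respond. It rests on a uniform, noise-free gain of about 3 points, and the 8-point row shows that a larger gain can register. Response also counts at any of the four post-baseline visits. Shares of 20% or 30% would give observed rates of 26.4% or 23.1% and early-stop probabilities of 22.1% or 36.6%, but nothing in the documents supports shares that high.

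The case for a change rests on the exposed position of the baseline in a trial without a control arm and on the low cost of the remedy, not on a demonstrated large bias.

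**What to change.** - Reconcile exclusion 8 with sections 5.0 and 6.0 by naming the enrolment step from which the 30 days are counted. The length of the period is not changed.
- State in 5.0.B that the baseline IIEF-5 used for the primary endpoint is completed within the PDE5-inhibitor-free period that exclusion 8 already sets and before the first dose of any study drug, and that an earlier form is repeated. The questionnaire appendix is not in the text reviewed, so its recall period should be checked against this wording.
- Extend 5.0.A.9 to record the date on which any ED treatment was last used.
- For men already enrolled (11 at the 2021 revision) whose baseline may predate the drug-free period, report the primary proportion with and without them.

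The cost is a sentence or two of protocol text, one date field, and an occasional repeat of a five-item questionnaire that section 5.0 already allows to be completed at home after remote consent. A few men may score differently on the repeat. Sample size, prior and stopping bounds are unaffected.

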## 1.0 TRIAL SUMMARY

Abbreviated Title	PAVE Therapy for Post-RT ED
Trial Phase	Phase II
Clinical Indication	Treatment of radiation-induced erectile dysfunction
Trial Type	Treatment
Type of control	Comparison to baseline in each patient
Route of administration	oral
Trial Blinding	NA
Treatment Groups	Three subgroups will be enrolled, patients who are not on any statins at the time of enrollment, those on atorvastatin, and those on other statins.
Number of trial subjects	50
Estimated duration of trial	4 years
Duration of Participation	1 year

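### Only PDE5 inhibitors are kept out of the baseline; other ED treatments are neither excluded nor required to be stable, so a change in their use can be counted as a PAVE result

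*Combined protocol and SAP*

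**What the plan says.** Section 1.0 gives the type of control as "Comparison to baseline in each patient"; there is no concurrent arm. Section 11.0 B.i scores a man as improved "if his score goes up enough to move at least 1 category less severe compared to baseline". Improvement at any visit is enough, and section 11.0 D adds that a responder never reverts.

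Two entry criteria bear on ED status and ED treatment at baseline. Inclusion 3 requires "Erectile dysfunction, as determined by an IIEF-5 score of <22". Exclusion 8 reads "Not currently taking a 5PDE inhibitor nor have used one within 30 days of enrolling in the study". No other criterion in section 4.0 restricts an ED drug or device. Inclusion 4 expressly admits men on testosterone replacement ("Normal testosterone (including men on testosterone replacement").

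The protocol expects other ED treatments in this population. Section 5.0 A.9 records "Most recent treatment tried for ED", and objective B.ii in section 3.0 is "To report the rate of choosing other ED treatments after PAVE". Section 5.0 A.8 says that "current medications including non-prescription substances will be recorded in the medical chart"; devices are not mentioned.

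After entry, section 11.0 B.iii collects prescribed ED medications at 18 months. Section 11.0 E reports how many men leave to start a prescription ED drug. Starting an ED treatment is not among the reasons for leaving the study in section 11.0 A.

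**The concern.** A before-and-after comparison within one man isolates PAVE only if nothing else that affects the score changes between the two measurements. Exclusion 8 protects the baseline from one class of treatment. For any other ED drug or device, the text supplied has no entry restriction, no stable-use requirement, no statement on whether IIEF-5 is scored with or without the aid, and no rule for scores obtained after an aid is started.

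A change in aid use can therefore act in either direction. A man who stops his aid after baseline is compared with an aided score, and a real PAVE gain may not show. A man who starts, resumes or increases an aid may rise a category, and one such visit makes him a responder for good. Both errors enter the primary proportion and the responder count used for futility.

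**Working it through.** **1. The plan's own figures.** Section 11.0 C uses N = 50 and a Beta(0.33, 0.67) prior, so with x responders the posterior is Beta(0.33 + x, 0.67 + 50 - x). Its equal-tailed 95% intervals are:

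- x = 16: 20.1% to 45.3%
- x = 17: 21.8% to 47.4%, half-width (47.4 - 21.8)/2 = 12.8 points

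Both match the plan. The stopping boundaries also reproduce: toxicity 6/10/14/17 and response 0/2/5/7 at 10/20/30/40 patients. Exact binomial enumeration over the four looks, with toxicity and response independent, gives Pr(stop early) at 10% toxicity of 0.814, 0.277 and 0.063 for response rates of 15%, 25% and 33%. The plan's table has 0.81, 0.28 and 0.06. At 10% toxicity nearly all of this is futility: the table's value at a 55% response rate is only 0.001.

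**2. Inputs the documents do not give.** Let f be the share of men who start, resume or increase an aid on study, and r the response rate among them. Both are assumed: f = 10% (range 5-20%) and r = 60-80%. With p the true PAVE rate,

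observed rate = (1 - f) × p + f × r.

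**3. Upward error, p = 25%** (below the plan's 33% minimum):

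| f | Observed, r = 60% | Observed, r = 80% | Pr(stop early) |
|---|---|---|---|
| 0 | 25.0% | 25.0% | 0.28 |
| 5% | 0.2375 + 0.03 = 26.75% | 0.2375 + 0.04 = 27.75% | 0.21 to 0.17 |
| 10% | 0.225 + 0.06 = 28.5% | 0.225 + 0.08 = 30.5% | 0.15 to 0.10 |
| 20% | 0.20 + 0.12 = 32.0% | 0.20 + 0.16 = 36.0% | 0.08 to 0.03 |

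**4. Upward error, p = 33%, f = 10%.** 0.297 + 0.06 = 35.7% and 0.297 + 0.08 = 37.7%, so the shift is 2.7 to 4.7 points.

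**5. Downward error, p = 33%.** In the worst case no man who uses an aid at baseline can register a response, so the observed rate is 0.33 × (1 - f), with f now the share of such men:

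- f = 5%: 31.4%, Pr(stop early) 0.09
- f = 10%: 29.7%, Pr(stop early) 0.12, a shift of 3.3 points
- f = 20%: 26.4%, Pr(stop early) 0.22

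**6. Aid used unchanged.** It is present in both scores. It may raise the baseline and leave less room to improve, which step 5 bounds, but it does not by itself produce a category gain.

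**The case against.** The strongest reply is that the endpoint is change from the man's own baseline. A reader might infer from exclusion 8 that any man on another ED aid is scored on his aid rather than on PAVE. The documents do not support that: constant use cancels in the comparison, and the IIEF-5 ceiling in inclusion 3 keeps out men whose aid already brings them to 22 or above. This stands, and it narrows the point to changes in use. It does not remove it, because a partly helped man can still enrol, change his use and gain a category.

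Second, a reader might take five users among 50 and infer a 10-point shift either way (5/50), nearly the 12.8-point half-width. That requires all five to be misclassified in the same direction. At a true 33%, five men contain on average 5 × 0.33 = 1.65 responders and 3.35 non-responders. Even if every one were misclassified, the expected limits are 1.65/50 = 3.3 points down and 3.35/50 = 6.7 points up. Likewise, one man can tip the 20-patient look (2 responders stop, 3 do not), but that is true of any misclassification at any boundary and says nothing specific about ED aids.

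Third, a reader might infer that widening exclusion 8 would settle the matter. An entry-only condition does not: a man who pauses his aid for entry has a lower baseline and may score a false response when he resumes. How long any treatment should be paused is also a clinical rule for the sponsor, not for a statistical review.

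Finally, the IIEF-5 questionnaire is in an appendix not in the text supplied, so any instruction there on aided scoring could not be checked.

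**Conclusion.** The point holds as a gap in the consistency of eligibility and in the response definition. Following the plan as written, a change in non-PDE5 aid use after baseline is scored as a PAVE result, and an upward error is never reversed. The likely size is moderate: on the central assumptions, about 3 to 5 points up at a true 33%, or at most about 3 points down. At a true 25%, the chance of an early stop roughly halves or more, from 0.28 to 0.15-0.10. These figures rest entirely on assumed values of f and r; the documents give neither, and at f = 20% the effect is about twice as large. The stated credible intervals, boundaries and operating characteristics are correct as calculated and do not depend on this gap. It is worth correcting because the correction is cheap and largely uses data the protocol already collects.

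**What to change.** 1. **Eligibility.** The sponsor should reconcile exclusion 8 with the protocol's own recognition of other ED treatments in section 5.0 A.9 and objective B.ii, so that baseline IIEF-5 is handled in the same way for all of them. Testosterone replacement, allowed by inclusion 4, stays outside this.
2. **Data.** Record current use of any ED drug or device at baseline and at each IIEF-5 visit, including whether it was started, stopped, resumed or increased since the last visit.
3. **Response definition.** In section 11.0 B.i, state that a category gain first seen after an aid was started, resumed or increased is not counted as a PAVE response. Apply the same definition to the futility count; the boundaries need no change.
4. **Analysis.** In section 11.0 E, report the ever-improved proportion with and without men using another ED aid at baseline.
5. **The 11 men enrolled at the 2021 revision.** Identify current users from A.8 and A.9 and confirm by query. A.9 alone does not separate current from past use, and A.8 does not mention devices.

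The cost is one data item per visit, one sensitivity row, a query for the men already enrolled, and possibly a slightly lower response rate or a few men excluded. The sample size and planned intervals are unaffected.

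### Section 4.0 does not explicitly exclude a man on a direct oral anticoagulant or heparin for a DVT, PE or MI more than 6 months old, or for an indication exclusions 9 and 10 do not name

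*Combined protocol and SAP*

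**What the plan says.** Four criteria in section 4.0 (Subject Exclusion Criteria) bear on antithrombotic drugs.

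- Exclusion 9: "No recent deep venous thrombosis, myocardial infarction or pulmonary embolism (within 6 months) requiring continued anticoagulation other than ASA".
- Exclusion 10: "No cardiac arrhythmias or artificial heart valves requiring anticoagulation other than ASA".
- Exclusion 11: "No concurrent drugs with anti-platelet properties (e.g., P2Y12 inhibitors, non-steroidal anti-inflammatory agents, selective serotonin reuptake inhibitors) other than low dose ASA (81mg/d").
- Exclusion 16: "No concurrent use of CYP1A2 inhibitors (e.g., ciprofloxacin), ketorolac, or vitamin K antagonists (e.g. warfarin").

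Exclusion 2 is a general clause: "No contraindication to an HMG-coA-reductase inhibitor, Vitamin E or Pentoxifylline". Two further exclusions concern bleeding or a bleeding source. Exclusion 4 reads "No recent cerebral or retinal hemorrhage that in the opinion of the treating physician would make PAVE unsafe (within 6 months") and exclusion 14 reads "No history of active peptic ulcer disease in the past 6 months".

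Section 7.0 C sets vitamin E at 1000 IU once daily, and section 11.0 B.ii puts active treatment at 1 year. Section 8.0 B lists bruising and bleeding among the possible effects of vitamin E. Section 5.0 C requires INR, PT and PTT before enrolment.

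**The concern.** Exclusions 11 and 16 work by drug. Exclusions 9 and 10 work by indication, and 9 also has a time window. Non-vitamin-K anticoagulants (direct oral anticoagulants, heparins) fall only under the second kind of rule, so a current user can fall outside all four criteria.

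This is a safety matter for the individual participant. The listed rules would let him add a year of high-dose vitamin E to an anticoagulant. The same list turns away men taking an SSRI or an NSAID, and men with a recent cerebral or retinal hemorrhage or active peptic ulcer. No sample size, endpoint or stopping boundary is involved.

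**Working it through.** The question is one of coverage, so the check is to run test cases against the four criteria. Each man has only the features stated.

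| Man | Excl. 9 | Excl. 10 | Excl. 11 | Excl. 16 | Result |
|---|---|---|---|---|---|
| Direct oral anticoagulant, PE 8 months ago | no (older than 6 months) | no | no (not a listed antiplatelet class) | no | not excluded |
| Warfarin, same PE | no | no | no | yes | excluded |
| Same direct oral anticoagulant, required for an arrhythmia | no | yes | no | no | excluded |
| Same direct oral anticoagulant, required for a PE within 6 months | yes | no | no | no | excluded |
| Heparin, indication not named in 9 or 10 | no | no | no | no | not excluded |
| SSRI or NSAID, no clot | no | no | yes | no | excluded |

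**Reading of exclusion 9.** The phrase about continued anticoagulation could qualify all three events or only PE. The first row is the same either way, because 9 reaches recent events only.

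**Count of indications for a non-vitamin-K anticoagulant.** Exclusion 9 names 3 (DVT, MI, PE), all limited to 6 months. Exclusion 10 names 2 (arrhythmia, artificial valve), with no limit. Total 3 + 2 = 5. Beyond 6 months, 2 of 5 remain barred and 3 of 5 do not. An indication outside the 5 is never barred. A vitamin K antagonist is barred for every indication at any time.

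**Other places that might close the gap.**

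- Section 5.0 A.8 says "current medications including non-prescription substances will be recorded in the medical chart". This records the drug but does not exclude the man.
- INR, PT and PTT are scheduled 6 times in Table 1 (baseline, 6 weeks, 3, 6, 9 and 12 months). None of the 3 tests has an eligibility limit. Testosterone, ALT/AST, CK and creatinine clearance each have one.
- Bleeding is among the CTCAE items in the Table 1 footnote. The first scheduled on-treatment check is at 6 ± 2 weeks, that is 4 to 8 weeks after he starts all three drugs.
- Section 8.0 E halves vitamin E for Grade 2 toxicity, and 8.0 F cuts pentoxifylline to 400 mg twice daily. If attribution is unclear, 8.0 G.3 reduces the statin first, pentoxifylline after 1 week and vitamin E after one more, so vitamin E is first reduced 1 + 1 = 2 weeks after the first step. Grade 3 or higher stops the drug, or all three if attribution is unclear, and removes the patient. All of these rules act after an event.
- The toxicity rule in 11.0 D counts at least possibly related Grade 3 or higher events in the first 8 weeks, starting with the first 10 patients. It protects the trial as a whole more than this man.

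**The case against.** The strongest reply is that nothing here is shown to be an error. The criteria do not contradict one another. The 6-month window in 9 may be deliberate, since 4 and 14 use the same window. Exclusion 16 may be a drug-interaction list, in which case its warfarin and ketorolac entries are weak evidence of a general bleeding screen. Exclusion 10 is tied to cardiac conditions, and cardiovascular signs have their own stopping rules in section 8.0. The screening physician has the medication list, hematologic history and coagulation tests before enrolment, and can use exclusion 2. A blanket bar would override the window in 9, make 9 and 10 largely redundant, and catch prophylactic heparin.

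Much of this stands. The intent behind 9 and 16 is not stated, and the gap is one of incomplete coverage. But exclusion 10 bars any anticoagulation other than ASA for its indications, whatever the drug and with no window, so the protocol's concern is neither specific to warfarin nor confined to recent events. Exclusion 2 leaves the decision to judgment, and the sponsor wrote 9, 10, 11 and 16 despite having it. Redundancy between criteria does no harm. The capture of prophylactic heparin is a real cost, though exclusion 16 already treats vitamin K antagonists without a dose qualifier.

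**Conclusion.** The gap is real and the criterion should be changed. On the visible text, current use of a non-vitamin-K anticoagulant is not explicitly barred for 3 of the 5 named indications once 6 months have passed, nor for any other indication at any time.

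The documents give no count of such men and no bleeding-risk comparison. I assume no share, and I do not claim that their risk equals that of the men who are excluded. The safety argument rests on the protocol's own listing of bleeding as a possible effect of vitamin E. The prescribing-algorithm figure and the appendices are not visible and could hold a further rule, so confidence is moderate. If such a rule exists, it belongs in section 4.0, where eligibility is decided.

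**What to change.** Leave exclusions 9, 10 and 11 as they are. In exclusion 16, after the vitamin K antagonist entry, add: *or any other anticoagulant (e.g., direct oral anticoagulants, heparins) for any indication; low-dose ASA (81 mg/d) is allowed*. This does not change how 9 treats a recent MI managed on ASA alone.

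The cost is one phrase in the next amendment and probably a few candidates, in a trial that was cut from 270 to 50 patients because accrual was slow (11.0 A). Prophylactic-dose heparin would also count. The needed data are already collected at baseline. If the sponsor did intend to admit men on these drugs after 6 months, section 4.0 should say so and give the reason.
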